1 SYNOPSIS

Name of Sponsor Company

Naurex, Inc, an affiliate of Allergan, plc.

Name of Finished Product Rapastinel (GLYX-13) Name of Active Ingredient

Open Label Extension for Subjects with Inadequate/Partial Response to Antidepressants during the Current Episode of Major Depressive Disorder Previously Treated with Rapastinel (GLYX-13) (Extension of GLYX13-C-202, NCT01684163)

Study No: GLYX13-C-203

Planned Number of Investigational Sites: 10 US sites

[figure not shown]
Clinical Phase: Phase 2

Objectives

Primary Objective:

The primary objective of this study is to examine the safety of long term repeat exposure to rapastinel (GLYX-13) in subjects who participated in GLYX13-C-202.

The primary endpoint is the number of participants who experience an adverse event over the course of the study.

Methodology:

Study Design:

Phase 2 open label safety study of rapastinel (GLYX-13) for participants who completed 12 weeks of treatment in GLYX13-C-202 (NCT01684163).

At the screening visit, the Structured Clinical Interview for Depression (SCID) will be administered to determine whether any exclusionary conditions have arisen since subject's completion of GLYX13-C-202.

A physical examination will be conducted to ascertain if significant changes have occurred since the subject ended participation in GLYX13-C-202. Blood and urine samples will be obtained for laboratory analysis. Antidepressant agents used since the subject ended participation in GLYX13-C-202 will be recorded.

On Week 1 Day 1, subjects will arrive at the investigative site having fasted for at least 10 hours, with water as desired. Each subject's eligibility will be confirmed; then a physical examination will be performed, and blood and urine samples for laboratory analysis will be obtained. Vital signs will be assessed and mass recorded. ECG will be recorded, the

Each subject will then receive an IV dose of rapastinel (GLYX-13) (225 mg or 450 mg unit dose) in a "slow bolus" injection in an upper extremity vein within approximately 1 to 2 minutes. Subjects will be discharged following determination by the investigator that they are medically able to leave.

Subjects will return to the study site during the first month on the schedule (weekly or biweekly) to which they were assigned in GLYX13-C-202. After the first month subjects will return to the study site on a

Name of Sponsor Company

Naurex, Inc, an affiliate of Allergan, plc.

Name of Finished Product

Rapastinel (GLYX-13)

Name of Active Ingredient

L-threonyl-L-prolyl-L-prolyl-L-threonine amide, acetate salt

schedule defined by treatment plan set by the investigator.

Rapastinel (GLYX-13) will be administered. Subjects will remain in the study unit until determination by the investigator that they are medically able to leave the study unit.

At the last visit of each quarter, the

ECG will be recorded and blood and urine samples will be obtained for laboratory analysis. Rapastinel (GLYX-13) will be administered. Subjects will remain in the study unit until determination by the investigator that they are medically able to leave.

Dose Level

Unit doses of rapastinel (GLYX-13), 225 mg/3 mL or 450 mg/3 mL IV, will be administered in a "slow bolus" injection to each subject in an upper extremity vein within approximately 1 to 2 minutes. Investigator will begin treatment based on the dose level (5 mg/kg or 10 mg/kg) to which the subject was assigned during participation in GLYX13-C-202; subjects originally assigned to 5 mg/kg will receive 225 mg/3 mL, and subjects originally assigned to 10 mg/kg will receive 450 mg/3 mL. If subject experiences adverse event(s) that the investigator believes may be associated with rapastinel (GLYX-13), the investigator may decrease dose level from 450 mg to 225 mg. If at any point the patient cannot tolerate the minimum 225 mg unit dose, the patient should be discontinued from the study.

Dose Interval

Dose interval for the first month of participation will be that (weekly or biweekly) to which the subject was assigned during the randomized withdrawal phase of GLYX13-C-202. The investigator will then formulate a treatment plan in which dose interval will remain the same or change. The treatment plan may be modified from time to time by the investigator if it is deemed prudent based on subject's depression status.

Treatment Plan

Following one month at the dose level (subjects who were assigned to placebo during the randomized withdrawal phase of GLYX13-C-202 are eligible to participate and will begin at the dose level to which the subject was assigned during the stabilization phase of GLYX13-C-202) and dose interval to which the subject was assigned during the randomized withdrawal period of GLYX13-C-202, the investigator may continue the same dose level and dose interval, or may change the dose level and dose interval. The investigator will complete a treatment plan that outlines the dose level and dose interval at which rapastinel (GLYX-13) will be administered. The investigator, at the investigator's discretion, may change the treatment plan to alter dose level and/or dose interval based on the subject's depression status.

Subject Participation:

Participation in the study may continue until rapastinel (GLYX-13) is approved for marketing in the U.S. or until the study is ended by the Sponsor.

Number of Subjects Planned

It is planned to enroll up to 100 subjects who participated in clinical study GLYX13-C-202.

Diagnosis and Main Criteria for Inclusion

Inclusion Criteria:

- 1. Participants who have completed 8 or more weeks of treatment in the preceding study (GLYX13-C-202, NCT01684163
- 2. Participants who wish to continue treatment with rapastinel (GLYX-13) after the

Name of Sponsor Company Naurex, Inc, an affiliate of Allergan, plc.	Name of Finished Product Rapastinel (GLYX-13)	Name of Active Ingredient L-threonyl-L-prolyl-L- threonine amide, acetate salt

preceding study

- 3. Meets Diagnostic and Statistical Manual, Fourth Edition, Text Revision (DSM-IV-TR) criteria for major depressive disorder (MDD)
- 4. Female subjects of childbearing potential with a negative serum pregnancy test prior to entry into the study and who are practicing an adequate method of birth control (eg oral or parenteral contraceptives, intrauterine device, barrier, abstinence) and who do not plan to become pregnant during the course of the study. Female subjects may be included without a negative serum pregnancy test if they are surgically sterile or at least 2 years post-menopausal.
- 5. Clinical laboratory values <2 times the upper limit of normal (ULN) or deemed not clinically significant per the investigator and medical monitor
- 6. Ability to understand the requirements of the study, provide written informed consent, abide by the study restrictions, and agree to return for the required assessments
- 7. Based on the investigator and medical monitor's clinical judgment, subjects with eating disorders, obsessive compulsive disorder (OCD), panic disorder, post-traumatic stress disorder (PTSD), and generalized anxiety disorders secondary to major depressive episodes (MDEs) are permitted.

Exclusion Criteria:

- Axis I diagnosis of delirium, dementia, dysthymia, amnestic or other cognitive disorder, schizophrenia or other psychotic disorder, bipolar I or II disorder, eating disorder (anorexia or bulimia nervosa), obsessive-compulsive disorder, panic disorder, acute stress disorder, agoraphobia, social phobia, attention-deficit hyperactivity disorder (ADHD), or PTSD
- 2. A clinically significant current Axis II diagnosis of borderline, antisocial, paranoid, schizoid, schizotypal, or histrionic personality disorder
- 3. Experiencing hallucinations, delusions, or any psychotic symptomatology in the current episode; lifetime history of psychosis
- 4. Huntington's, Parkinson's, Alzheimer's, Multiple Sclerosis, or a history of seizures or strokes
- 5. Currently hospitalized or residing in an in-patient facility during study participation
- 6. Substance abuse since the end of participation in GLYX13-C-202, including greater than or equal to 5 units of alcohol per day where 1 unit = ½ pint of beer, 1 glass of wine 4 oz, or 1 oz, of spirits consumed most weeks or in the opinion of the investigator
- 7. Women who are planning to become pregnant during the course of the study
- 8. Allergy or intolerance to current antidepressant or other current medications
- 9. Participation in any clinical trial of an investigational product or device within 30 days of enrollment in this trial with the exception of GLYX13-C-202.
- 10. Positive screen for drugs of abuse: cocaine, marijuana, PCP, ketamine, opioid or other agent that in the opinion of the investigator is being abused
- 11. Pose current (past 6 months) suicide risk based on administration of the C-SSRS and the investigator's clinical judgment
- 12. Human immunodeficiency virus (HIV) infection (based on the based on the HIV-1 & HIV-2 antibody screen) or other ongoing infectious disease

Name	of Sponsor	Company
------	------------	---------

Naurex, Inc, an affiliate of Allergan, plc.

Name of Finished Product Rapastinel (GLYX-13)

Name of Active Ingredient L-threonyl-L-prolyl-L-prolyl-Lthreonine amide, acetate salt

Test Product: rapastinel (GLYX-13) (150 mg/mL in water for injection)

Dose and Mode of Dosing:

IV Dosage:

[figure not shown]
- 225 mg dose in 3 mL with rapastinel concentration 75 mg/mL
- 450 mg dose in 3 mL with rapastinel concentration 150 mg/mL

Study drug will be administered in a "slow bolus" injection to each subject in an upper extremity vein within approximately 1-2 minutes.

Duration of Dosing:

Each subject will receive doses of rapastinel (GLYX-13) until ending participation in the study or until GLYX-13 is approved for marketing in the U.S.

Criteria for Evaluation:

Safety

All reported AEs

[figure not shown]

Statistical Methods and Data Analysis

Descriptive statistics will be presented for all efficacy and safety parameters. No inferential statistical analyses will be performed.

All safety parameters will be summarized for the Safety Population, defined as all subjects who received any injection of study drug.

Efficacy parameters will be summarized for the full analysis set (FAS), defined as all subjects who received any injection of study drug and who have at least one post-baseline efficacy assessment.

3 LIST OF ABBREVIATIONS AND DEFINITION OF TERMS

ADT Antidepressant treatment

ADHD Attention-Deficit Hyperactivity Disorder

AE adverse event

ATC Anatomical Therapeutic Chemical Classification

CRF case report form

CRO Clinical Research Organization

CTCAE Common Terminology Criteria for Adverse Events

DMID Division of Microbiology and Infectious Diseases

DSM-IV-TR Diagnostic and Statistical Manual, Fourth Edition, Text Revision

ECG Electrocardiogram

eCRF electronic case report form

FDA Food and Drug Administration

GCP Good Clinical Practices

HIV human immunodeficiency virus

ICF informed consent form

ICH International Conference on Harmonization

IV Intravenous

IWRS interactive web response system

LSMs least square means

MedDRA Medical Dictionary for Regulatory Activities

MDD major depressive disorder
MDEs major depressive episodes
MTD maximum tolerated dose

NaCl sodium chloride

NCI National Cancer Institute

NMDAR N-methyl-D-aspartate receptor

NR2B NMDA receptor 2B

PTSD Post-Traumatic Stress Disorder

QID-SR Quick Inventory of Depressive Symptomatology Self Report

Q-LES-Q SF Quality of Life Enjoyment and Satisfaction Questionnaire Short Form

SAE serious adverse event SAP Statistical analysis plan

SCID Structured Clinical Interview for Diagnostic and Statistical Manual (DSM) of

Mental Disorders

4 INTRODUCTION

The rationale for evaluating rapastinel (GLYX-13) in subjects with treatment-resistant depression results from recent studies using ketamine, a N-methyl-D-aspartate receptor (NMDAR) channel blocker, and CP-101,606, a competitive NMDAR antagonist. Both of these agents are efficacious in animal models and human diseases in which NMDAR have been implicated, but both suffer psychotomimetic effects that render them impractical to use for chronic therapy. When administered as single intravenous (IV) doses to subjects with treatmentresistant depression, the NMDAR antagonists ketamine (channel blocker) and CP-101,606² (NMDA receptor 2B [NR2B] competitive antagonist) induced significant, rapid antidepressant effects that lasted for several days following single doses, even though both of these agents, like rapastinel (GLYX-13), have short plasma half-lives. In subjects who received ketamine in a crossover study compared to placebo, improvement in depression scores was apparent at first assessment (40 minutes following dose); this improvement remained significant throughout the following week. Of 17 subjects treated with ketamine, 71% responded (> 50% reduction in depression score) and 29% experienced remission (depression score < 7) by 24 hours. At 1 week, 35% of responders maintained response following the single dose. Psychotomimetic effects were apparent at 40 minutes.

In a study in subjects who had failed paroxetine (the lead-in period of the trial), subjects who received a single intravenous (IV) dose of CP-101,606 showed improvement in depression scores compared to placebo at Day 5 (primary endpoint). Of 15 subjects treated with CP-101,606, 60% responded, and 33% experienced remission. Of responders, 78%, 58%, 42% and 30% maintained response on Days 8, 12, 15, and 30. Psychotomimetic effects were observed in many of the subjects who received CP-101,606. Thus, single IV doses of ketamine or CP-101,606 caused rapid, sustained reductions in depression despite plasma half-lives of 2 hours.

These studies are particularly interesting from the perspectives of medical need and commercial opportunity since the onset of action of existing antidepressant drugs is 2 weeks or longer and about one-half of subjects do not achieve a response to the first drug tried. About 30% of subjects do not respond to any of multiple drugs tried. In contrast, ketamine and CP-101,606 both produced responses in most subjects, even though all of these subjects had failed at least 2 other antidepressant drugs. Further, the onset of antidepressant action was rapid, within hours

for ketamine. Either of these effects in a drug that can be used therapeutically (neither ketamine nor CP-101,606 can be due to their psychotomimetic side effects) would be an advance in therapeutics.

Rapastinel (GLYX-13) is an NMDAR glycine site functional partial agonist.³ IV administration of rapastinel (GLYX-13) results in rapid antidepressant-like activity in the Porsolt assay in rats without changes in locomotor activity or inhibition of prepulse inhibition that predict psychotomimetic side effects in humans.³ In rats and normal human volunteers, rapastinel (GLYX-13) exhibits plasma half-life of less than 10 minutes following IV administration. In a phase 2a study (GLYX13-C-201) in subjects with MDD who had failed (< 25% improvement using the ATRQ) at least one antidepressant agent during the current episode in whom all

antidepressant agents had been washed out for 14 days, a single IV dose of rapastinel (GLYX-13), 5 mg/kg or 10 mg/kg, reduced compared to placebo within one day and activity lasted for 7 days, but not 14 days. Psychotomimetic side effects assessed using the BPRS+ scale were not observed in any subjects.

This protocol will now explore fixed IV doses of 225 mg (to replace 5 mg/kg) and 450 mg (to replace 10 mg/kg). In previous studies, rapastinel (GLYX-13) has been studied at dose levels up to 30 mg/kg IV and was found to be well tolerated.

5 STUDY OBJECTIVES

5.1 Primary Objective

The primary objective of this study is to examine the safety of long term repeat exposure to rapastinel (GLYX-13) in subjects who participated in GLYX13-C-202.

The primary endpoint of this study is to examine the number of participants who experience an adverse event over the course of the study.

6 STUDY DESIGN

[figure not shown]
6.1 Overall Study Design

This is a phase 2 open label safety study of GLYX-13 for participants who completed 12 weeks of treatment in GLYX13-C-202 (NCT01684163).

At the screening visit, the Structured Clinical Interview for Depression (SCID) will be administered to determine whether any exclusionary conditions have arisen since subject's completion of GLYX13-C-202. A physical examination will be conducted to ascertain if significant changes have occurred since the subject ended participation in GLYX13-C-202. Blood and urine samples will be obtained for laboratory analysis. Antidepressant agents used since the subject ended participation in GLYX13-C-202 will be recorded.

On Week 1, subjects will arrive at the investigative site having fasted for at least 10 hours, with water as desired. Each subject's eligibility will be confirmed; then a physical examination will be performed, and blood and urine samples for laboratory analysis will be obtained. Vital signs will be assessed and mass recorded. ECG will be recorded,

Each subject will then receive an IV dose of rapastinel (GLYX-13), 225 mg or 450 mg (replaces 5 mg/kg or 10 mg/kg, respectively) in a "slow bolus" injection in an upper extremity vein within approximately 1 to 2 minutes. Subjects will be discharged following determination by the investigator that they are medically able to leave.

ECG will be recorded and blood and urine samples will be obtained for laboratory analysis. Rapastinel (GLYX-13) will be administered. Subjects will remain in the study unit until determination by the investigator that they are medically able to leave.

6.2 Dose Level

Unit doses of rapastinel (GLYX-13), 225 mg/3 mL or 450 mg/3 mL IV, will be administered in a "slow bolus" injection to each subject in an upper extremity vein within approximately 1 to 2 minutes. Investigator will begin treatment based on the dose level (5 mg/kg or 10 mg/kg) to which the subject was assigned during participation in GLYX13-C-202; subjects originally assigned to 5 mg/kg will receive 225 mg/3 mL, and subjects originally assigned to 10 mg/kg will receive 450 mg/3 mL. If subject experiences adverse event(s) that the investigator believes may be associated with rapastinel (GLYX-13), the investigator may decrease dose level from 450 mg to 225 mg. If at any point the patient cannot tolerate the minimum 225 mg unit dose, the patient should be discontinued from the study.

6.3 Treatment Plan

Following one month at the dose level (subjects who were assigned to placebo during the randomized withdrawal phase of GLYX13-C-202 are eligible to participate and will begin at the dose level to which the subject was assigned during the stabilization phase of GLYX13-C-202) and dose interval to which the subject was assigned during the randomized withdrawal period of GLYX13-C-202, the investigator may continue the same dose level and dose interval, or may change the dose level and dose interval. The investigator will complete a treatment plan that outlines the dose level and dose interval at which rapastinel (GLYX-13) will be administered. The investigator, at the investigator's discretion, may change the treatment plan to alter dose level and/or dose interval based on the subject's depression status.

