Investigator will begin treatment based on the dose level (5 mg/kg or 10 mg/kg) to which the subject was assigned during participation in GLYX13-C-202; subjects originally assigned to 5 mg/kg will receive 225 mg/3 mL, and subjects originally assigned to 10 mg/kg will receive 450 mg/3 mL. If subject experiences adverse event(s) (AEs) that the investigator believes may be associated with rapastinel (GLYX-13), the investigator may decrease dose level from 450 mg to 225 mg. If at any point the subject cannot tolerate the minimum 225 mg unit dose, the subject should be discontinued from the study. There are 3 dose groups (despite weekly or biweekly dosing schedule):

- Low dose group consisting of all subjects whose dose level is 225 mg or 5 mg/kg;
- High dose group consisting of all subjects whose dose level is 450 mg or 10 mg/kg;
- Mixed dose group consisting of all subjects who changed dose level between low dose (225 mg or 5 mg/kg) and high dose (450 mg or 10 mg/kg).

At the screening visit, the Structured Clinical Interview for Depression (SCID) will be administered to determine whether any exclusionary conditions have arisen since subject's completion of GLYX13-C-202. The Columbia Suicide Severity Rating Scale (C-SSRS) will be administered. A physical examination will be conducted to ascertain if significant changes have occurred since the subject ended participation in GLYX13-C-202. Blood and urine samples will be obtained for laboratory analysis. Antidepressant agents used since the subject ended participation in GLYX13-C-202 will be recorded.

[figure not shown]
On Week 1 Day 1, subjects will arrive at the investigative site having fasted for at least 10 hours, with water as desired. Each subject's eligibility will be confirmed; then a physical examination will be performed, and blood and urine samples for laboratory analysis will be obtained. Vital signs will be assessed and mass recorded. Electrocardiogram (ECG) will be recorded,

Each subject will then receive an intravenous (IV) dose of rapastinel (GLYX-13) (225 mg or 450 mg unit dose) in a "slow bolus" injection in an upper extremity vein within approximately 1 to 2 minutes. Subjects will be discharged following determination by the investigator that they are medically able to leave. The aforementioned procedures must be repeated within 24 hours before dosing if screening assessments were performed greater than 7 days before study drug dosing.

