4.1 SAFETY POPULATION

The Safety Population will consist of all subjects who received any injection of study drug. All safety analyses will be based on this population.

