9.0 SAFETY ANALYSES

The safety analysis will be performed using the Safety Population.

The safety parameters will include AEs, clinical laboratory, vital signs, and ECG parameters. For each safety parameter, the last non-missing safety assessment before the first dose of study drug in study GLYX13-C-203 will be used as the baseline for all analyses of that safety parameter.

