9.1 ADVERSE EVENTS

AEs will be coded using the *Medical Dictionary for Regulatory Activities* (MedDRA).

An AE (classified by preferred term) will be considered a treatment emergent adverse event (TEAE) if it was not present before the first dose of study drug or was present before the date of the first dose of study drug and increased in severity during the study period till the end of participation. If more than 1 AE was reported before the first dose of study drug and coded to the same preferred term, then the AE with the greatest severity will be used as the benchmark for comparison with the AEs occurring during the study. An AE that occurs more than 30 days after the date of the last dose of study drug will not be considered as a TEAE. An AE that becomes serious on or after the first dose of study drug will also be considered as TEAE.

The number and percentage of subjects reporting TEAEs will be tabulated by SOC and preferred term and further categorized by severity and causal relationship to study drug. If more than 1 AE is coded to the same preferred term for the same subject, the subject will be counted only once for that preferred term using the greatest severity and strictest causality for the summarization by severity and causal relationship. The distribution of TEAEs by severity and relationship to study drug will be summarized. An AE that occurs more than 30 days after the date of the last dose of study drug will not be summarized.

The incidence of common (in \geq 2% of subjects) TEAEs during the study period till the end of participation will be summarized by preferred term and will be sorted by decreasing frequency.

An SAE that occurred between the date of the first dose of study drug and 30 days after the date of the last dose of study drug, inclusive, will be considered a treatment-emergent SAE (TESAE). The number and percentage of subjects who have TESAEs will be summarized by preferred term. In addition, the incidence of on-therapy SAEs that led to death will be summarized separately by preferred term.

The incidence of TEAEs leading to premature discontinuation of study drug during the study period till the end of participation will be summarized by preferred term, and will be sorted by decreasing frequency.

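### Persistent drug effects carried into C-203 unchanged are not treatment-emergent, but count if they return after placebo withdrawal; the visible SAP pools both groups, so their reported incidence depends on the roll-over mix

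*Protocol*

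**What the plan says.** **Who enters.** Protocol 6.3 provides that "subjects who were assigned to placebo during the randomized withdrawal phase of GLYX13-C-202 are eligible to participate and will begin at the dose level" used in the stabilization phase. SAP 2.0 also recognises that entrants had received rapastinel or placebo in C-202.

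**How they are grouped.** SAP 4.1: "The Safety Population will consist of all subjects who received any injection of study drug". SAP 2.0 defines groups by dose level alone: "There are 3 dose groups (despite weekly or biweekly dosing schedule"), namely low, high and mixed. Disposition, baseline characteristics, exposure and compliance (SAP 5.0 to 7.2) are overall, with population counts also by center. In SAP 9.1, "The number and percentage of subjects reporting TEAEs will be tabulated by SOC and preferred term", then by severity and causality. None of these displays uses the C-202 withdrawal assignment.

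**What baseline is.** SAP 9.0: "the last non-missing safety assessment before the first dose of study drug in study GLYX13-C-203 will be used as the baseline". This applies to every subject.

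**What counts.** Under SAP 9.1, an event that predates dosing is treatment-emergent only if it "was present before the date of the first dose of study drug and increased in severity during the study period", with one addition: "An AE that becomes serious on or after the first dose of study drug will also be considered as TEAE". Protocol 12.7 works the same way at collection: a condition that existed before dosing is recorded as an AE only if its frequency, intensity or character gets worse. That rule bears on the primary endpoint (Protocol 5.1), the number of participants with an AE.

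**The concern.** Entrants arrive in two different states. Those from the placebo arm of the withdrawal phase have had a period off drug and are re-exposed. Those from the rapastinel arm may arrive still carrying drug effects.

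The baseline and TEAE rules are the same for everyone, but they turn on the subject's state at the first C-203 dose. A persistent effect that a continuing subject brings in unchanged is invisible to the TEAE tables. The same effect, if it resolved on placebo and comes back, is counted. For effects of that kind a pooled percentage describes neither restarting nor continuing. It is a weighted average whose weight is the share of restarters, and no visible display reports that share.

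The study's only stated objective is long-term safety and it has no concurrent control. A reader of the preferred-term tables could take a diluted figure for a low risk. The same would hold for mean changes from baseline, unless the SAP sections that are not visible already split them.

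**Working it through.** The plan has no figure to reproduce. Protocol 14.4 and SAP 12.0 give only a cap of 100 subjects, and the Protocol synopsis rules out inferential analysis. The check is a mixture calculation on assumed inputs.

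**Inputs**
- w, the share of entrants from placebo withdrawal: not stated; assumed 0.10 to 0.67 (two thirds).
- q, the incidence of a persistent drug effect while on drug: not stated; assumed 5%, 10% or 20%.
- f, the fraction of that effect already present and unworsened at the first C-203 dose in continuing subjects: not stated; 0, 0.5 or 1.
- Restarters are assumed to have lost the effect before the C-203 baseline.
- From the documents: at most 100 subjects, and a common-TEAE table with a 2% threshold (SAP 9.1), that is 2 of 100.

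**Step 1: pooled incidence.** Pooled = q × [w + (1 − w) × (1 − f)].

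| q | f | w = 0.10 | w = 0.25 | w = 0.50 | w = 0.67 |
|---|---|---|---|---|---|
| 5% | 1 | 0.5% | 1.25% | 2.5% | 3.3% |
| 10% | 1 | 1.0% | 2.5% | 5.0% | 6.7% |
| 20% | 1 | 2.0% | 5.0% | 10.0% | 13.3% |
| 10% | 0.5 | 5.5% | 6.25% | 7.5% | 8.3% |
| 10% | 0 | 10% | 10% | 10% | 10% |

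The last row marks the limit of the point: if nothing is carried into baseline, the mix does not matter. A separate restarter column would show q at every w.

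**Step 2: the common-TEAE table.** With f = 1, reaching 2% in expectation needs w ≥ 0.02/q: 0.40, 0.20 and 0.10 for q = 5%, 10% and 20%. For q = 5%, the chance that at least 2 subjects are counted is 1 − 0.95^n − n × 0.05 × 0.95^(n−1), where n is the number of restarters among 100 subjects:
- n = 10: 0.09
- n = 25: 0.36
- n = 50: 0.72
- effect counted in all 100: 0.96

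**Step 3: the any-AE count.** Let b be the share with some new-onset AE in either group. With f = 1 and independence, pooled = b + w × (1 − b) × q.
- b = 80%, q = 10%: 0.80 + w × 0.02, so 80.2% at w = 0.10 and 81.3% at w = 0.67.
- b = 30%, q = 20%: 0.30 + w × 0.14, so 31.4% and 39.3%.

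**Step 4: mean change from baseline.** A sustained shift d that is fully in the continuing subjects' baseline and absent from the restarters' gives a pooled mean change of w × d, that is 10% to 67% of d over the same range of w.

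**The case against.** The case against is substantial and narrows the point.

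- **Scope of the rule.** A reader might infer that a drug effect is counted in one group and excluded by rule in the other. SAP 9.1 does not say that. It counts new-onset, worsened and newly serious events in both groups. Restarters had earlier exposure in the stabilization phase and may also carry effects into baseline. SAP 9.1 also does not say plainly whether a resolved earlier event of the same preferred term is present before dosing. This stands: only persistent, unworsened effects are at issue.
- **The gap between studies.** A reader might infer that the rapastinel subjects never stopped. The documents do not establish this. Protocol 6.1 asks about conditions and antidepressant use since C-202 ended, and gives no interval. The Protocol introduction reports a plasma half-life under 10 minutes and single-dose activity at 7 but not 14 days. After a long gap both groups could start off drug and the asymmetry would shrink. This stands.
- **Randomization.** A reader might infer that comparing the groups recovers a nearly unconfounded randomized contrast. It does not. Entry required at least 8 weeks of C-202 treatment, a wish to continue and renewed eligibility (Protocol 7.1, 7.2), all of it selection after treatment. This stands.
- **The first month.** Protocol 6.2 allows AE-driven dose reduction with no first-month exception, so the dose may respond to the outcome being tabulated. This stands as a caveat on any first-month display.
- **Visibility.** The laboratory, vital-sign, ECG and efficacy analysis sections are not visible and may contain a split. This stands for mean changes. It does not reach the AE section, which is visible and has none.
- **Preference.** The pooled count describes the enrolled cohort, which is the stated endpoint of a descriptive study. That is fair for the any-AE count. It does not help someone reading preferred-term incidences as risks.

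**Conclusion.** The point holds in limited form. On the visible text, subjects from rapastinel and subjects from placebo withdrawal are pooled, and an effect carried unchanged into C-203 is treated differently from the same effect reappearing on restart. Preferred-term incidences for such effects therefore depend on the roll-over mix. Mean changes would too, if the sections not visible have no split.

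The size cannot be fixed: the restarter share, the AE rates and the gap between studies are not given. Under full carry-over the reported incidence is w × q, which can keep a 5% effect out of the common-TEAE table. With no carry-over there is no distortion. The primary any-AE count may move by about one percentage point if background incidence is high, and by more if it is low. This merits a change to the displays; it does not undermine the pooled analysis as a description of the cohort.

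**What to change.** In SAP 9.1, add descriptive columns by C-202 withdrawal-phase assignment (placebo, rapastinel) beside the overall column, for TEAEs with onset in the first month and for TEAEs overall. Do the same in the change-from-baseline displays if they lack it. Report the number of subjects in each group and, where available, the time since the last C-202 rapastinel dose. State that the contrast is descriptive and not a randomized comparison because entry was selective, and that AE-driven dose reduction is permitted in the first month.

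The baseline, the TEAE definition and the pooled results stay as they are. The columns show the re-exposure experience undiluted; they do not recover an effect already in the continuing subjects' baseline.

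The cost is SAP wording, table columns and carrying the assignment into the analysis dataset. Protocol 6.3 already requires the assignment to be known. The downside is small cells.
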